## 9.2 Outcomes

### 9.2.1 Primary outcome

The primary outcome will be clinical increase in zone (width) of keratinized mucosa (KM). For edentulous sites, KM width will be measured by determining the distance from the crest of the edentulous ridge to the mucogingival line to the nearest millimeter with a Castroviejo caliper. For patients with an existing implant or tooth, KM width will be measured from the implant mucosal or tooth margin to the mucogingival line.

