### Design and Outcomes

This is a randomized, parallel-group phase II study to assess EVPOME vs. POM to determine differences in the primary efficacy measure of increased keratinized mucosa; secondary measures of graft contracture and Wound Healing Index; and ancillary outcome measures of tissue perfusion measured graft color and laser Doppler flowmetry, and postoperative pain.

Primary outcome measure: Clinical increase in zone (width) of keratinized mucosa (KM). For edentulous sites, KM width will be measured by determining the distance from the crest of the edentulous ridge to the mucogingival line to the nearest millimeter with a Castroviejo caliper. For patients with an existing implant, KM width will be measured from the implant mucosal margin to the mucogingival line. The amount of attached gingival tissue (keratinized) will be evaluated using a calibrated periodontal probe measured to nearest 0.5mm.

Secondary outcome measures: Graft contracture will be measured in mesio-distal and corono-apical directions. Post-surgical measurements of the graft site will be taken at visits 5, 6, 7, and 8, and will be compared to the original graft size to assess percentage of graft contracture. Wound Healing Index (WHI) will be recorded after surgery using the following criteria:

- Score 1= uneventful healing with no gingival edema, erythema, suppuration, patient discomfort, or flap dehiscence
- Score 2 = uneventful healing with slight gingival edema, erythema, patient discomfort, or flap dehiscence, but no suppuration
- Score 3 = poor wound healing with significant gingival edema, erythema, patient discomfort, flap dehiscence, or any suppuration

Ancillary outcome measures: Laser Doppler flowmetry (LDF) measurements will be used

to assess graft blood flow (tissue perfusion of the grafts).

Graft color is correlated to vascular perfusion and thus can give us an indication of graft vascularity. Finger pressure will be applied in the center of the graft for 15 seconds and/or until tissue blanching. The pressure will then be released and the time for the tissue to return to its previous color will be recorded. If the tissue returns to its previous color within 15 seconds, this will be recorded as positive graft vascularity. If not, then it will be recorded as negative graft vascularity.

Overall postoperative pain will be assessed via a visual analog scale (VAS).

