### 6.3.5 Clinical Assessments

Clinical assessments include width of keratinized mucosa (KM) as determined by the distance between the crest of the edentulous ridge, the gingival margin of the tooth, or the implant mucosal margin and the mucogingival line to the nearest millimeter, graft contracture, graft color as determined by assessing tissue perfusion, postoperative pain, Wound Healing Index (WHI), color of graft tissue compared to surrounding

3/28/2017

non-grafted tissue, and oral care follow-up. These assessments will be performed at post-operative visits 5, 6, 7 and 8. Periodontal measures include Periodontal Pocket Depth (PPD – measured from gingival margin to base of periodontal pocket to nearest millimeter), gingival recession measured from cemento-enamel junction on tooth to gingival margin, Clinical Attachment Level (CAL- determined by subtracting the gingival recession from PPD), and bleeding on probing (BOP) determined as present (1) or absent (0),

Visual analog scale for pain will be assessed for groups, I (at time of harvest of biopsy and EVPOME placement) and group II at time of harvesting of palatal donor graft and grafting at recipient site.

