## 9.5 Data Analyses

The main aim of the study is to determine by quantitative outcome measures that EVPOME will function as well as POM in terms of increased epithelialized tissue, decreased contracture, and increased microvessel infiltration. It is also expected that the EVPOME will have a closer adaptation in color rendition to the surrounding tissue. Our primary comparisons will be based on the observations at four weeks post-graft.

**AIM 1 - Keratinized Tissue:** Primary comparison will be based on week 4 assessment using an equivalence test of means. Background data on measurements of keratinized tissue for POM (standard of care) gave a mean measurement of 3.70 mm with an SD of 0.65 mm. The mean and SD were relatively constant over the follow up period from 3 to 12 months. If, in this study, both EVPOME and POM give comparable results, the distribution of the mean difference in keratinized tissue with 30 subjects in each arm will be approximately normal with a mean of 0 and standard error of 0.17, and a 95% confidence interval for the true mean difference between the two procedures will have a margin of error of about 0.33 mm. This confidence interval will exclude a value for the mean difference of 0.55mm or larger with probability at least 80%. Therefore sample size will be adequate to show near equivalence of the two treatments if the degree of keratinized tissue measurement of EVPOME is within  $\pm 0.55$ mm of POM. Statistical power will be even larger if non-inferiority of EVPOME to POM is desired, where true increase in keratinized zone in EVPOME group is no less than 0.55 mm compared with the increase of zone of keratinized tissue in POM.

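### Keratinized-mucosa width is read to 1 mm in the body text, with an unreconciled 0.5 mm reading in the synopsis; this is coarse for a ±0.55 mm equivalence margin, and one 0.5 mm rule would improve power at almost no cost.

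*Combined protocol and SAP*

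**What the plan says.** The reading rule for the primary outcome appears in three places.

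- **Section 9.2.1 (Primary outcome).** The outcome is the increase in width of keratinized mucosa (KM). At edentulous sites a caliper is used: "KM width will be measured by determining the distance from the crest of the edentulous ridge to the mucogingival line to the nearest millimeter". For implant or tooth sites it gives the landmarks but no resolution and no instrument.
- **Section 6.3.5 (Clinical Assessments).** Width runs from the ridge crest, "the gingival margin of the tooth, or the implant mucosal margin and the mucogingival line to the nearest millimeter". This is a 1 mm rule for all three site types.
- **Synopsis, Design and Outcomes.** It repeats the 1 mm caliper rule for edentulous sites and then adds: "The amount of attached gingival tissue (keratinized) will be evaluated using a calibrated periodontal probe measured to nearest 0.5mm".

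Section 9.5, AIM 1, plans an equivalence test of means at Week 4. The background data on palatal grafts "gave a mean measurement of 3.70 mm with an SD of 0.65 mm". With 30 per arm the text gives a standard error of 0.17 mm and a 95% margin of error of about 0.33 mm, and concludes: "This confidence interval will exclude a value for the mean difference of 0.55mm or larger with probability at least 80" percent. It does not say at what resolution the background data were read, and it does not mention rounding.

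**The concern.** There are two linked problems.

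First, the instructions are not reconciled. The synopsis sentence concerns attached tissue, with keratinized in brackets. It is unclear whether this is the same quantity as the crest-or-margin to mucogingival-line width, a second measure, or the reading meant for tooth and implant sites. Staff reading the synopsis and section 9.2.1 together could reasonably record some subjects in 1 mm steps and others in 0.5 mm steps.

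Second, 1 mm is coarse for the question asked. The unit exceeds the planning SD of 0.65 mm, and the trial must place a confidence interval for a mean difference inside ±0.55 mm. Rounding adds variance and widens that interval, so two truly equivalent grafts become more likely to miss the primary criterion. Because the outcome is an increase, the screening reading may carry rounding error as well as the Week 4 reading. Digits lost to rounding cannot be recovered after data collection.

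**Working it through.** **Inputs.** SD 0.65 mm, mean 3.70 mm, 30 per arm, true difference 0, two-sided 95% interval and margin ±0.55 mm (all section 9.5, AIM 1). Reading units are 1 mm (sections 6.3.5 and 9.2.1) and 0.5 mm (synopsis).

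**Formulas.** SE = SD × √(2/30). Power = 2Φ(0.55/SE − 1.96) − 1. Rounding to a unit h adds about h²/12 to the variance per reading: 1/12 = 0.0833 mm² for 1 mm, and 0.25/12 = 0.0208 mm² for 0.5 mm.

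**Plan's own figure.** SE = 0.65 × 0.2582 = 0.168 and 1.96 × 0.168 = 0.329, matching the stated 0.17 and 0.33. Power = 2Φ(3.277 − 1.96) − 1 = 2 × 0.9061 − 1 = 81.2%. The stated 80% reproduces. Thirty per arm is the smallest number that reaches it, so there is no slack.

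**Coarseness.** If widths are normal with mean 3.70 and SD 0.65, the share of 1 mm readings equal to 3, 4 or 5 is Φ((5.5 − 3.7)/0.65) − Φ((2.5 − 3.7)/0.65) = Φ(2.77) − Φ(−1.85), about 96%.

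**Power by what 0.65 mm contains**

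| Case | Variance (mm²) | SD (mm) | SE (mm) | Power |
|---|---|---|---|---|
| 0.65 already contains the trial's 1 mm rounding | 0.4225 | 0.650 | 0.168 | 81.2% |
| 0.65 contains none; one 1 mm reading | 0.4225 + 0.0833 = 0.5058 | 0.711 | 0.184 | 69.9% |
| 0.65 contains none; two 1 mm readings | 0.4225 + 0.1667 = 0.5892 | 0.768 | 0.198 | 58.5% |
| 0.65 contains one 0.5 mm rounding; one 1 mm reading | 0.4225 − 0.0208 + 0.0833 = 0.4850 | 0.696 | 0.180 | 72.8% |
| 0.65 contains one 0.5 mm rounding; two 1 mm readings | 0.4225 − 0.0208 + 0.1667 = 0.5683 | 0.754 | 0.195 | 61.3% |

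The two-reading rows take 0.65 mm as the SD of the change and treat the two rounding errors as independent.

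**Check by simulation.** Rounding simulated normal data directly gave 69.6% (one 1 mm reading) and 58.1% (two) with the 1.96 multiplier, and 67.8% and 55.8% with t intervals. The change simulation assumed a baseline mean of 2 mm and SD of 0.7 mm.

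**Effect of reading to 0.5 mm**

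- If 0.65 mm contains no rounding, one reading: variance 0.4225 + 0.0208 = 0.4433, SD 0.666, power 78.5%, against 69.9% at 1 mm. For two readings: variance 0.4642, SD 0.681, power 75.7%, against 58.5%.
- If 0.65 mm already contains one 1 mm rounding: variance 0.4225 − 0.0833 + 0.0208 = 0.3600, SD 0.600, SE 0.155, power 2Φ(3.550 − 1.96) − 1 = 88.8%, against 81.2% at 1 mm.

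**Sample size alternative.** If 0.65 mm contains no rounding and the 1 mm unit is kept, reaching 80% takes 36 per arm (one reading) or 41 per arm (two).

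**The case against.** The strongest objection is that no loss of power has been shown. The 0.65 mm figure is an observed SD of recorded measurements, so it already carries some reading error. If those data were read like the trial's analysed quantity, power stays at about 81%. This stands: a reader might infer from the 70% and 58% rows that rounding will take power well below 80%, but the documents do not give the resolution of the source data and cannot support that.

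The 58% end needs more still. Section 9.5 gives 0.65 mm beside a mean of 3.70 mm that hardly moved from 3 to 12 months, which reads as the SD of a follow-up width and not of a change. Applying such an SD to an increase is a separate question, and its effect depends on a baseline correlation that the documents do not give.

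A reader might also infer that a unit larger than 0.55 mm makes equivalence untestable. It does not. The margin spans 1.10 mm from end to end, which is wider than the unit, and it applies to a difference between means of 30 per arm. At a true difference of zero the cost is precision, not bias.

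The size also depends on the test rule. With a 90% interval (two one-sided 5% tests), power is 89.7% with no added rounding, 82.3% with one 1 mm reading and 74.2% with two. For one-sided non-inferiority at 0.025, which section 9.5 also mentions, it is 90.6%, 85.0% and 79.3%. The power statement in section 9.5, however, is built on the 95% interval.

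Finally, section 6.3.5 supplies the 1 mm unit that section 9.2.1 omits for tooth and implant sites, so the body text does not itself instruct mixed units. The departure is one synopsis sentence, possibly about a separate measure. That narrows the inconsistency but does not remove it, because nothing says how that reading relates to the primary outcome.

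**Conclusion.** The point holds as a cheap and worthwhile improvement to the primary measurement, not as a demonstrated failure of the sample size. Two things are established with high confidence: the 1 mm and 0.5 mm instructions are not reconciled, and 1 mm is coarse beside an SD of 0.65 mm and a margin of ±0.55 mm.

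The size of any power loss is conditional. Under the plan's 95% interval, with 30 per arm and a true difference of zero, power is about 58% to 81%. It is 81% if 0.65 mm already includes the same rounding and 70% if it includes none and one reading is rounded. It is 58% only if 0.65 mm includes none, is the SD of the change, and two readings are rounded independently. The case for changing the unit does not depend on which of these is true, because a 0.5 mm reading raises power in each.

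**What to change.** - **Synopsis, section 6.3.5 and section 9.2.1:** state one rule. KM width is measured from the crest or margin to the mucogingival line and read to 0.5 mm at every site type, with the same instrument for a given subject at screening and at all follow-ups.
- **Synopsis:** say whether the attached-tissue probe reading is a separate measure, and if so that it is not the primary outcome, or delete the sentence.
- **Section 9.5, AIM 1:** state whether 0.65 mm is the SD of a width or of a change and at what resolution it was read, and restate the power for the analysed quantity on that basis.

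The cost is protocol wording, a CRF field with one decimal place and slightly longer measurement at visits already scheduled. No extra staff, visits or subjects are needed, and the synopsis already names a probe read to 0.5 mm. Duplicate readings are optional and not needed for this fix.

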### 9.2.2 Secondary outcomes

The secondary outcome will include percent graft contracture and wound healing index. Graft contracture will be measured in mesio-distal and coronal-apical directions. Post-surgical measurements of the graft site will be taken at visits 5, 6, 7, and 8 (Weeks 2, 4, 8, and 24), and will be compared to the original graft size to assess percentage of graft contracture. Photographs of the surgical site will be taken.

Wound Healing Index (WHI) will be recorded after surgery using the following criteria:

- Score 1 = uneventful healing with no gingival edema, erythema, suppuration, patient discomfort, or flap dehiscence
- Score 2 = uneventful healing with slight gingival edema, erythema, patient discomfort, or flap dehiscence, but no suppuration
- Score 3 = poor wound healing with significant gingival edema, erythema, patient discomfort, flap dehiscence, or any suppuration

### 9.2.3 Ancillary outcomes

Ancillary outcome will include assessment of blood flow (tissue perfusion of the grafts) via laser Doppler flowmetry (LDF) evaluation, graft color, postoperative

pain, histology, and immunohistochemistry (IHC) to evaluate graft revascularization.

Graft color is correlated to vascular perfusion and thus can give us an indication of graft vascularity. Finger pressure will be applied in the center of the graft for 15 seconds and/or until tissue blanching. The pressure will then be released and the time for the tissue to return to its previous color will be timed. If the tissue returns to its previous color within 15 seconds, this will be recorded as positive graft vascularity. If not, then it will be recorded as negative graft vascularity.

Overall postoperative pain will be assessed via a visual analog scale (VAS).

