## 2.2 Supporting Data

A previous Phase I clinical trial demonstrated the safety and efficacy of EVPOME to increase keratinized gingival tissue without adverse events or local complications. This study achieved its main objectives and informed the design of the prospective clinical trial described here. For the phase I clinical trial, the researchers did not receive approval to have a control group (i.e., AlloDerm® without cultured primary oral keratinocytes), since the study was done to determine safety of the EVPOME and not efficacy. Thus, no post-operative biopsy specimens were obtained to assess vascularization of the tissue or persistence of the grafted cultured cells. Also note that while the previous study was performed using AlloDerm® as the scaffold upon which the EVPOME is constructed, this study will use AlloPatch® which is very similar to AlloDerm®. AlloPatch® must be used in this study because AlloDerm® is no longer available.

Previous studies showed that the grafted EVPOMEs had a deeper red hue than AlloDerm® grafts at post-operative day 6. This observation suggests that the grafted EVPOMEs revascularized faster than AlloDerm® grafts. In addition, there was histologic and immunohistochemical documentation of microvessel ingrowth into the underlying dermal component, AlloDerm®, of the EVPOME in a study of severe combined immunodeficient mice. It can therefore be reasonably stated that the grafted EVPOME had undergone revascularization by postoperative days 7 to 14.

The previously mentioned completed Phase I clinical trial was distinctive from other case studies using tissue-engineered products because it was conducted under our CBER/FDA-approved, investigator-initiated IND 10118. The IND required specific and rigorous cell testing and monitoring of the biologic product. Glucose consumption was selected as the functional test because it was considered a good indicator of the number of viable cells present on the EVPOME. Glucose consumption could detect cellular variations within EVPOME grafts, even in material from the same individual. As such, this functional test addresses the quality assurance/control and the release criterion mandated by CBER/FDA.

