#### 6.2.5 **Visit 5: Post-operative (Post-grafting)**

Routine post-operative visits at Week 2 +/- 3 days post-grafting will include an oral examination and clinical assessments, including degree of epithelialization and percent contracture.

Measurement of the maximum distance between the peripheral borders of the graft in both the x and y axis will be taken to assess percent of graft contracture. Laser Doppler flowmetry measurements will be taken with the pre-fabricated template at the approximate geometric center of the graft and on the contralateral side of the jaw as the graft placement. This will be done after stent removal. per this protocol:

LDF measurements will be with the subject resting in supine position, and at a

room temperature. A flexible probe (PR407, Perimed) will be used to obtain the measurements. The flowmeter will be calibrated before taking any measurements. Gingival blood-flow data will be reported in perfusion units (PU) and collected on the wideband setting. Voltage output values will be stored on an encrypted PC computer for storage and subsequent analysis.

Intraoral photographs will be taken. A visual analog scale of pain will be taken, and subjects will also be questioned about any adverse events.

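### Graft vascularity is timed in seconds but scored only as positive or negative at 15 seconds, and no analysis of the times is planned

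*Combined protocol and SAP*

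**What the plan says.** The Synopsis (Design and Outcomes) and section 9.2.3 describe the same test. Finger pressure is held on the center of the graft for 15 seconds and/or until it blanches, then released, and the return of color is timed. The Synopsis says that "the time for the tissue to return to its previous color will be recorded"; section 9.2.3 says that "the time for the tissue to return to its previous color will be timed" and does not say that the time is kept. Both then define a two-way score. In section 9.2.3: "If the tissue returns to its previous color within 15 seconds, this will be recorded as positive graft vascularity". Any slower return counts as negative.

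Section 6.3.5 lists graft color among the clinical assessments and gives the schedule: "These assessments will be performed at post-operative visits 5, 6, 7 and 8", that is, Weeks 2, 4, 8 and 24. Section 9.5 gives no test, effect size or power for this outcome, either as a score or in seconds. Its mixed-model paragraph for repeated measures cites pain and the Wound Healing Index as examples and does not mention graft vascularity.

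**The concern.** A quantity that is already measured on a continuous scale has no planned use beyond a split at 15 seconds. A split treats a graft that refills in 2 seconds and one that refills in 14 seconds as the same result. The protocol expects EVPOME to be ahead of POM in early microvessel ingrowth (section 6.2.6), and a chairside refill time is one of the few repeated measures that could show this. If many grafts in both arms fall on the same side of the cut, the two percentages will look alike even when one arm refills faster, and the result could be read as similar vascularity. An analysis of the seconds chosen after the data are seen would be post hoc.

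**Working it through.** **Inputs from the documents.** 30 subjects per arm (section 3; section 9.3 allows for up to 6 dropouts by enrolling 66). The cut is at 15 s. No share positive, effect size or SD is given for this outcome.

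**Benchmark effect.** The nearest stated figure is for ordinal vascular ingrowth in section 9.5: SD 1 unit, 30 per arm, 80% power at the 0.05 level (taken as two-sided).
- Standard error = 1 × √(2/30) = 0.258.
- Margin of error = 1.96 × 0.258 = 0.506 (stated 0.51).
- Detectable difference = (1.96 + 0.84) × 0.258 = 0.723 (stated 0.72).

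The plan's figure is reproduced. A t-test at the same size detects 0.74 SD. I therefore assume a shift of 0.72 to 0.74 SD in refill time, borrowed as a benchmark only.

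**Information lost by the cut.** For a normal latent scale and a small shift, the efficiency of a split that leaves a share p positive is φ(z_p)² / [p(1 − p)].
- p = 50%: 0.3989² / 0.25 = 0.637, loss 36%.
- p = 75%: 0.3178² / 0.1875 = 0.539, loss 46%.
- p = 80%: 0.2800² / 0.16 = 0.490, loss 51%.
- p = 90%: 0.1755² / 0.09 = 0.342, loss 66%.
- p = 95%: 0.1031² / 0.0475 = 0.224, loss 78%.

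The loss is never below 36%, and it passes half only at about 80% positive.

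**Power at 30 per arm, two-sided 5%.** The EVPOME share positive is Φ(Φ⁻¹(p_POM) + d). Yes/no power is for the uncorrected two-proportion test, summed exactly over all outcome tables. Rank power is for a Wilcoxon rank-sum test with all times over 15 s tied, from 10,000 simulations per row (error about one point). Each cell gives d = 0.72 / d = 0.74.

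| POM positive | EVPOME positive | Yes/no power | Rank power |
|---|---|---|---|
| 50% | 76% / 77% | 57% / 59% | 72% / 75% |
| 60% | 84% / 84% | 53% / 55% | 74% / 76% |
| 75% | 92% / 92% | 43% / 45% | 75% / 77% |
| 90% | 98% / 98% | 20% / 21% | 75% / 78% |
| 95% | 99% / 99% | 5% / 5% | 76% / 78% |

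The gain is about 15 points at the even split (72 − 57) and about 71 to 73 points at 95% (76 − 5 and 78 − 5). The usual normal-approximation formula gives 15% rather than 5% in the last row; it is unreliable that close to 100%, so the exact figure is used. Fisher's exact test on the score would do worse (about 47% in the top row and below 1% in the bottom row at d = 0.72).

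**Timing error.** Rounding to whole seconds alone changes rank power little. With an added error of 1 to 2 s and log-SDs of 0.3 to 1.0 (assumed), rank power with POM at 95% positive falls to roughly 47% to 73%. At the even split, 1 to 2 s of error gives about 61% to 74%. That still exceeds the error-free yes/no figures, by only a few points at worst.

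**The case against.** The strongest reply is that the documents do not show the score to be near its ceiling. A reader might infer a ceiling from section 2.2, which says that "the grafted EVPOME had undergone revascularization by postoperative days 7 to 14", since section 6.2.5 puts the earliest graft-color reading at "Routine post-operative visits at Week 2 +/- 3 days post-grafting", or days 11 to 17. That inference goes too far. The timeline covers EVPOME only. It rests on graft hue at day 6 and on histology "in a study of severe combined immunodeficient mice", with AlloDerm as scaffold, whereas this trial uses AlloPatch. It gives no refill time, no POM timeline and no share positive. Nor would a ceiling in one arm be enough: with EVPOME at 95% and POM at 60%, the yes/no comparison has 94% power, and with POM at 70% it has 78%. This part of the objection stands.

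A reader might also infer that most of the information is thrown away. That needs about 80% or more positive, which the documents do not state. The Synopsis says the time is recorded, so the seconds may well survive for analysis; the CRF is not in the documents.

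Two further points stand. The plan specifies no comparison of this outcome, so the power figures describe the natural analysis of the defined score, not one that the plan contains. And the consequence is limited. The outcome is ancillary and missing from the ancillary list in section 9.3. Laser Doppler flowmetry and immunohistochemistry address the same question. The color rendition in the superiority hypothesis appears to be the match to surrounding tissue, which section 6.3.5 lists separately.

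The objection does not remove the main point. The score is less efficient than the times at every split tried, including the even one, so the case for using the seconds needs no ceiling.

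**Conclusion.** The point holds as a cheap improvement of minor severity. The only defined graft-vascularity score is a split at 15 s of a time that is already taken, and no analysis of that time is planned. The cost is at least about 36% of the information, and at 30 per arm about 15 points of power at an even split, rising steeply if most grafts in both arms are positive. These sizes rest on a normal latent scale, a shift of 0.72 to 0.74 SD borrowed from the ingrowth endpoint, a single-visit comparison and accurate timing; none of these is stated for this outcome. Whether the score will be near its ceiling is unknown. The primary and secondary conclusions are not affected.

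**What to change.** Align the Synopsis and section 9.2.3 so that both say that the refill time in seconds is recorded on the CRF and is the graft-vascularity outcome, with >15 s as the censored category. In section 9.5, compare the arms at Week 4 with a Wilcoxon rank-sum test (or a log-rank test censored at 15 s), and report median times by arm at Weeks 2, 8 and 24. Keep the 15-second positive/negative split as a descriptive summary.

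The cost is one numeric CRF field and a few lines of protocol text. The reading is already taken and timed, so no visit, procedure or staff is added. The downsides are a small hand-timing error and a summary slightly less simple than a percentage.
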